Testing the Impact of Two Posters on Contraceptive Knowledge, Contraceptive Preferences, and Perceived Pregnancy Risk

NCT number NCT03372369

Document Date December 22, 2017

Primary Investigator [name] PhD

Co-Primary Investigator [name] [name]

Co-Investigators [name]; [name];

[name]; [name]

[name], PhD

Study Design

We survey women before and after random administration of one of two educational posters informing readers about contraception. Baseline data for both groups will be collected on our three outcomes: contraceptive knowledge, willingness to use effective contraception, and perceived pregnancy risk. Participants will then be randomly shown one of the two fact sheets. Then post-exposure questions on the three outcomes will be asked.

Comparators

Shown in Figures 1 and 2 are the two posters that will be tested in this clinical trial.

[figure not shown]
Procedures

We will use Amazon Mechanical Turk to recruit participants.

The survey will first be tested with N=20 participants using the procedures described below. This will be done to estimate the length of time necessary to complete the survey so that accurate time estimates can be provided to potential participants. This will also enable the researchers to ensure that any technical problems with the survey are corrected before the main research data is collected. Data collected in this phase will not be analyzed unless no changes are made to the study materials after reviewing the data.

Once the survey procedures are tested, we will recruit approximately N=1000 participants to complete the survey (final N=990).

Figure 1: CDC Contraceptive Poster

CS 242797

U.S. Department of
Health and Human Services
Centers for Disease
Control and Prevention

CONDOMS SHOULD ALWAYS BE USED TO REDUCE THE RISK OF SEXUALLY TRANSMITTED INFECTIONS.

Other Methods of Contraception

[figure not shown]
Lactational Amenorrhea Method: LAM is a highly effective, temporary method of contraception.

Emergency Contraception: Emergency contraceptive pills or a copper IUD after unprotected

intercourse substantially reduces risk of pregnancy.

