pregnant or avoid pregnancy?”³ We measured past pregnancy scares by asking: “Have you ever had a pregnancy scare; that is, thought you were pregnant when you didn’t want to be, but later discovered that you weren’t pregnant after all?” We measured numeracy using the Berlin single item numeracy scale.⁴ This scale has been tested and validated to show that people who answer this question correctly are in the top 50% of the population in numeracy.⁴ Data were also collected on the sexes of the woman’s past sex partners, whether she had ever seen the poster before, and whether there were any types of birth control the woman could not use for health/safety or cost reasons. The following variables were measured using questions from the National Survey of Family Growth (NSFG): biological sex, age, whether the participant was trying to conceive or was currently pregnant, sexual intercourse in the past three months, education, time since first sex, and marital status. Finally, the following variables were measured using questions from the National Longitudinal Survey of Adolescent to Adult Health (Add Health): race/ethnicity (Wave V), income (Wave IV), relationship status (Wave IV), and health insurance type (Wave IV).

Analysis

We first tested whether the demographic and other factors were balanced between our randomized groups using two-sample t-tests and likelihood-ratio tests as appropriate. We did not find any statistically significant imbalances for any of the variables. We conducted two-sample t-tests on the change in the mean score for each of our outcomes to test whether each poster improved the three primary outcomes relative to baseline and in comparison to the other poster. We used the Bonferroni correction to account for multiple comparisons. Using the

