same methods, we also tested the hypothesis that the three pre-specified subgroups (low numeracy, pregnancy scares, and no birth control) had greater increases in their mean scores for the patient-centered poster versus the CDC poster. We chose these subgroups because the patient-centered poster was designed to appeal to the needs of these groups. Finally, because correct answers to some of the questions on the Contraceptive Knowledge Assessment were not given by either poster, we could determine the proportion of the change in contraceptive knowledge that was attributable to the posters. We did this by analyzing the change in contraceptive knowledge separately for questions that did and did not have the correct answer provided by either poster. All analyses were conducted in Stata (Stata/SE 15, College Station, TX, US).

For our power calculations, we assumed an alpha of 1% and a power of 80%. For our final analysis sample of N=936, comparing the two posters we can detect a 3 percentage point difference in mean change in contraceptive knowledge (standard deviation of 0.18¹), a 0.8 percentage point difference in accuracy of perceived pregnancy risk (standard deviation of 0.05), and a 6 percentage point difference in the mean change in effectiveness of most likely contraceptive method (standard deviation of 0.35⁵).

References

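### The subgroup t-tests compare the posters only within each targeted group, so they cannot show that the new poster's advantage is larger there than in other women

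*Combined protocol and SAP*

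**What the plan says.** The Analysis section names one method for the outcome comparisons: "We conducted two-sample t-tests on the change in the mean score for each of our outcomes", comparing each poster with baseline and with the other poster. It adds: "We used the Bonferroni correction to account for multiple comparisons". The number of comparisons covered is not stated.

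The subgroup analysis follows directly, using the "same methods, we also tested the hypothesis that the three pre-specified subgroups (low numeracy, pregnancy scares, and no birth control"). The hypothesis is that these women "had greater increases in their mean scores for the patient-centered poster versus the CDC poster". The reason given is: "We chose these subgroups because the patient-centered poster was designed to appeal to the needs of these groups".

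No interaction term, no analysis of women outside a subgroup, no subgroup sizes and no subgroup power appear anywhere in the document. The power statement at the end of the Analysis section covers the whole sample only: "For our final analysis sample of N=936, comparing the two posters".

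**The concern.** The rationale is one of targeting: the poster was built for women with low numeracy, a past pregnancy scare or no current method. A natural question is whether the poster difference is larger in these women than in the rest. A t-test confined to the subgroup uses no data from the other women, so it cannot separate two situations:

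- the new poster is better by the same amount for everyone;
- the new poster is better mainly, or only, for the women it was designed for.

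Either can produce a significant subgroup result. Without the estimate for the complement beside it, a reader who knows the rationale could take such a result as confirming the targeted design. In the other direction, a small subgroup can miss significance through lack of numbers and be reported as not helped. The comparison of the posters in the whole sample is not affected.

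**Working it through.** **Inputs from the document (Analysis section).** Analysis sample 936; alpha 1%; power 80%; knowledge SD 0.18; stated detectable knowledge difference 3 percentage points ("points" below).

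**Assumptions.** Equal allocation, 468 per poster (Study Design says "Participants will then be randomly shown one of the two fact sheets" but gives no ratio). Two-sided tests (sidedness is not stated). Subgroup shares: only low numeracy has an anchor, near 50%, from the description of the numeracy item under Measures. The others are not given, so a range is shown.

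**Step 1, the plan's own figure.** Detectable difference = (2.576 + 0.842) × SD × √(2/468). For knowledge, SE = 0.18 × √(2/468) = 0.01177, and 3.417 × 0.01177 = 0.040, or 4.0 points. The stated 3 points is not reproduced on these assumptions; power at 3 points is about 49%. That is a separate matter and does not affect this point. Below, 3 points serves only as a benchmark effect.

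**Step 2, one within-subgroup test under a uniform 3-point benefit.** For share p, SE = 0.18 × √(2/(468p)), and the chance of a significant favourable result is Φ(0.03/SE − 2.576).

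| Share p | SE | Chance of significance |
|---|---|---|
| 10% | 0.0372 | 4% |
| 15% | 0.0304 | 6% |
| 20% | 0.0263 | 8% |
| 50% | 0.0166 | 22% |
| 70% | 0.0141 | 33% |

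For a 15% subgroup and a true 4-point benefit the chance is about 10%, so a real benefit there would usually be missed.

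**Step 3, at least one of three subgroups.** If the tests at 50%, 50% and 15% were independent, the chance would be 1 − 0.78 × 0.78 × 0.944 = 0.43. The subgroups overlap, so the tests share women and are positively correlated. Simulation with 4,000 trials, normal change scores and independent subgroup membership gives about 37%. Other assumed shares (50/50/20, 50/50/10 and 50/30/10%) give 31% to 37%. With larger uniform benefits and shares of 50/50/15%, the figure is about 60% at 4 points and 84% at 5 points.

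**Step 4, the interaction under the same uniform benefit.** Each two-sided 1% interaction test favours the subgroup 0.5% of the time, so three give about 3 × 0.5% = 1.5%. Simulation gives 1.3% to 1.9%. This rate is fixed by construction; it shows that the interaction asks a different question, not that it is more powerful.

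**Step 5, what the interaction can detect.** SE = 0.18 × √(2/(468p) + 2/(468(1−p))). At p = 50% this is 0.0235, twice the main-effect SE, so 80% power needs 3.417 × 0.0235 = 8.0 points of difference between the poster effects. The figure is 8.8 points at 30%, 10.0 or 10.1 at 20% depending on rounding, and 13.4 at 10%.

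**The case against.** The strongest reply is that the stated hypothesis compares poster with poster inside the subgroup and names no other group of women. Whether the new poster beats the CDC poster in the women it was made for is a legitimate pre-specified question, and a within-subgroup t-test answers it. This stands.

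Three stronger readings are tempting, and the document does not support them.

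- A reader might infer that the plan claims special benefit in the targeted groups. It does not. That reading comes from the rationale sentence, which says only what the poster was designed to do.
- A reader might take the 37% as an error rate. It is not. If the poster helps all women it does help the targeted women, and a significant subgroup test is then correct. It becomes misleading only when presented as evidence of a larger effect than in others.
- A reader might suppose that a uniform benefit always makes the subgroup tests significant, or that these tests are irrelevant to the design rationale. Step 2 gives 22% at a 50% share and 6% at 15% for a 3-point effect. A benefit within the subgroup is also relevant to the rationale; it is just not sufficient to show targeting.

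Two further replies have force. The plan's Bonferroni correction would lower the rates: with an assumed family of nine tests (three outcomes by three subgroups, 0.05/9), the 50% subgroup at 3 points falls from 22% to about 17%, and at least one success in three from 37% to about 30%. It changes the threshold but not the question tested. And low precision counts more heavily against the interaction than against the subgroup tests: a 3-point differential at a 50% share has only about 10% power. The argument for the interaction is therefore that it addresses the differential question, not that it detects more.

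**Conclusion.** The point holds as a limit on what the subgroup analyses can support. They are valid for the literal hypothesis and uninformative on whether the poster difference is larger in the targeted women than in others, and nothing in the text warns against the second use. That conclusion follows from the method named and needs no assumption about effect or subgroup size.

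The illustrative size does rest on assumptions: about 37% of trials with at least one favourable subgroup under a uniform 3-point knowledge benefit (31% to 37% across the shares tried), given SD 0.18, 468 per arm, two-sided 1% tests and independent subgroup membership. Only knowledge was simulated. This is a worthwhile improvement to a secondary set of analyses, not a defect in the main comparison.

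**What to change.** For each outcome and each subgroup, fit one linear model in all analysed women with poster, subgroup indicator, poster × subgroup and the baseline score. From it:

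- report the poster difference with its confidence interval in the subgroup and in its complement;
- base any claim of greater benefit in a targeted group only on the interaction estimate and its confidence interval;
- keep the within-subgroup comparisons as the answer to the literal hypothesis, stating that they are not evidence of differential benefit;
- state how many comparisons the Bonferroni correction covers and whether the interactions are among them.

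The interaction term is the essential part. The baseline score is an additional modelling choice, since the main t-tests are unadjusted.

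The cost is a few sentences of analysis text and nine models (three outcomes by three subgroups), using variables the plan already measures. The real downside is imprecision: at N=936 the knowledge interaction needs about 8 points for 80% power at a 50% share and about 13 at 10%. Fewer subgroup claims will be possible, and the report should say that a non-significant interaction does not show the absence of a differential effect.

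### The detectable differences printed for comparing the two posters do not follow from the stated alpha, power, sample size and standard deviations

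*Combined protocol and SAP*

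**What the plan says.** The last paragraph of the Analysis section gives the power statement. It opens "For our power calculations, we assumed an alpha of 1% and a power of 80" per cent, without saying whether the alpha is one-sided or two-sided. It then says "For our final analysis sample of N=936, comparing the two posters" and gives three detectable differences:

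- Knowledge: "comparing the two posters we can detect a 3 percentage point difference in mean change in contraceptive knowledge", SD 0.18.
- Accuracy of perceived pregnancy risk: 0.8 percentage points, SD 0.05.
- Effectiveness: "a 6 percentage point difference in the mean change in effectiveness of most likely contraceptive method", SD 0.35.

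Earlier in the same section the test is named: "We conducted two-sample t-tests on the change in the mean score for each of our outcomes". Study Design says "Participants will then be randomly shown one of the two fact sheets" but gives no allocation ratio. Procedures says "we will recruit approximately N=1000 participants to complete the survey (final N=990"), so 936 is the total over both posters and cannot be the size of one arm.

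**The concern.** A detectable difference for a two-sample comparison is fixed by alpha, power, arm sizes and the SD. All of these are printed except the allocation and the sidedness, so the three figures can be checked. All three come out too small, by a similar factor, which suggests one common cause rather than a slip in a single number.

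Poster against poster is the randomised question, and this paragraph is the only place where the plan says how small a difference it could find. A reader of a null result would take it that differences of 3, 0.8 and 6 points would have been found with 80% probability. On the printed inputs that probability is close to one half.

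**Working it through.** **Inputs.** From the power paragraph: alpha 0.01, power 0.80, N = 936 in total, SDs 0.18, 0.05 and 0.35. From the Analysis section: two-sample t-test on change. Two assumptions, because the document is silent: arms of 468 each (the most favourable split), and SDs that are SDs of the change score.

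**Detectable difference.** Δ = (z for alpha + z for power) × SD × √(2/n per arm), with √(2/468) = 0.0654.

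- Two-sided 1%: (2.576 + 0.842) × 0.0654 = 0.2234, multiplied by each SD.
- One-sided 1%: (2.326 + 0.842) × 0.0654 = 0.2071, multiplied by each SD.

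| Percentage points | Knowledge | Accuracy | Effectiveness |
|---|---|---|---|
| Printed | 3 | 0.8 | 6 |
| Two-sided 1%, 468 per arm | 4.02 | 1.12 | 7.82 |
| Ratio to printed | 1.34 | 1.40 | 1.30 |
| One-sided 1%, 468 per arm | 3.73 | 1.04 | 7.25 |

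The exact noncentral t gives 4.03, 1.12 and 7.83 two-sided, so the normal approximation is not the cause.

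**Power at the printed differences** (noncentral t, 934 degrees of freedom): 49%, 45% and 52% two-sided; 59%, 55% and 62% one-sided. For 80% power two-sided, n per arm = 2 × (3.417 × SD/Δ)², which is 841, 913 and 795, against 468 available.

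**Readings that might close the gap but do not.**

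- Rounding: at the upper rounding limits of the printed values (3.5, 0.85 and 6.5 points), power is 65%, 51% and 60% two-sided; 74%, 61% and 70% one-sided.
- N = 990 (495 per arm): two-sided Δ is 3.91, 1.09 and 7.60, with power 52%, 47% and 55%; one-sided power is 62%, 57% and 64%.
- Unequal arms make it worse: 312 against 624 gives about 4.3, 1.2 and 8.3 two-sided.
- All allowances together (one-sided, N = 990, SDs at their lower rounding limits of 0.175, 0.045 and 0.345): 3.52, 0.91 and 6.95, still above 3.5, 0.85 and 6.5, though knowledge only just.

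**Settings that give the printed values after rounding.**

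| Setting, 80% power | Knowledge | Accuracy | Effectiveness |
|---|---|---|---|
| Two-sided 1%, 936 per arm, or one-sample with n = 468 | 2.84 | 0.79 | 5.53 |
| One-sided 5%, 468 per arm | 2.93 | 0.81 | 5.69 |

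Two-sided 5% with 468 per arm gives 3.30, 0.92 and 6.41, which misses the printed 0.8.

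**If the SDs are single-time SDs.** Then SD of change = SD × √(2(1 − r)), where r is the pre-post correlation. For 80% power at the printed differences (two-sided 1%, 468 per arm) the SD of change must be Δ/0.2234 = 0.134, 0.036 and 0.269. Solving r = 1 − (SD of change/SD)²/2 gives 0.72, 0.74 and 0.71. Power at the printed differences then depends on r:

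| r | Knowledge | Accuracy | Effectiveness |
|---|---|---|---|
| 0.25 | 31% | 28% | 33% |
| 0.50 | 49% | 45% | 52% |
| 0.75 | 85% | 81% | 87% |

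**The case against.** The strongest reply is that the document never says what the SDs measure. Two of them are cited to outside papers and may be single-time SDs. One common correlation of about 0.71 to 0.75 then yields all three printed values after rounding (two-sided), and about 0.66 to 0.71 is enough one-sided. Measures says the scores were taken immediately before and after the poster, so a high correlation is plausible. On that view an input is missing and the arithmetic may be sound.

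This stands as a possibility and is why the cause cannot be named. It does not rescue the paragraph as written. No correlation appears anywhere in the document, and the SDs for knowledge and effectiveness are printed directly beside differences in mean change. If a correlation was used, the claim depends on a figure the reader is not given.

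A second objection is that the recomputed figures inherit doubtful inputs. Accuracy is scored 0 or 1 at each time, so its change is −1, 0 or 1. An SD of 0.05 means a variance of 0.0025, or about 0.25% of women changing, roughly 2 of 936. Effectiveness is scored 0 to 3, so a percentage point has no defined meaning there. Both remarks are correct. The 1.1 and 7.8 points show what the printed inputs imply; they are not endorsed as realistic.

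A third objection is that the effect is small: the paragraph seems to have been written around an achieved sample. That is fair, and it limits the matter to reporting and interpretation.

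**Conclusion.** The concern holds. With alpha 1%, 80% power, 936 women in two equal arms and the printed SDs taken as change-score SDs, the detectable differences are 4.0, 1.1 and 7.8 points two-sided (3.7, 1.0 and 7.2 one-sided), not 3, 0.8 and 6. The two-sided values are 1.30 to 1.40 times the printed ones. The equal-arm assumption favours the plan. The change-score assumption is the one that matters: without it, the printed figures need a correlation that the document does not give. The source of the discrepancy cannot be determined from the text. No estimate, test or p-value is affected, and nothing shows that this paragraph set recruitment. It should be corrected because it misstates, on its own inputs, what the randomised comparison could detect.

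**What to change.** In the power paragraph, first state the sidedness of the 1% alpha, the allocation, and for each SD whether it is a single-time or a change-score SD and on which scale. Then do one of the following:

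- Restate the between-poster detectable differences as 4.0, 1.1 and 7.8 points (two-sided 1%, 80% power, 468 per arm, printed SDs as change-score SDs).
- Keep 3, 0.8 and 6 points and state power of about 49%, 45% and 52%.
- If the figures were meant for change within one poster, or rest on a pre-post correlation or another alpha, label them so and print that input.

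In every case, recompute the accuracy figure if the SD of 0.05 is revised. The cost is one or two sentences, with less favourable figures or one added input. No extra enrolment is proposed and no analysis changes.

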Finally, accuracy of perceived pregnancy risk was assessed by comparing a woman’s current contraceptive method to her perceived pregnancy risk. Perceived pregnancy risk was measured using the following question: “What is your chance of getting pregnant this year?” with possible responses being very high (score = 5, annual pregnancy risk >50%), high (4, annual pregnancy risk 25-50%), moderate (3, annual pregnancy risk 5-25%), low (2, annual pregnancy risk 1-5%), and very low (1, annual pregnancy risk ≤1%). We assessed the accuracy of perceived risk based on the most effective birth control method a woman used in the past three months. In accordance with the WHO categories², for highly effective methods, we coded an accurate perception to be very low risk; for effective methods, an accurate perception was low or moderate risk; for less effective methods, an accurate perception was moderate or high risk; for no method, an accurate perception was very high risk. An accurate perception was assigned a score of 1 and an inaccurate perception, 0. Our accuracy in perceived pregnancy risk outcome was the change in this score between baseline and follow-up.

Baseline data were collected on factors that might influence these outcomes. We measured prospective pregnancy intentions with the question, “Are you currently trying to get

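### Accuracy of perceived pregnancy risk: the stated SD of 0.05 and detectable difference of 0.8 points cannot both hold for a −1/0/+1 change score, because 0.8 points needs a pooled SD of at least 0.063

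*Combined protocol and SAP*

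**What the plan says.** The Measures section defines the outcome in two steps. At each time point, "An accurate perception was assigned a score of 1 and an inaccurate perception, 0". Then, "Our accuracy in perceived pregnancy risk outcome was the change in this score between baseline and follow-up". The Analysis section gives the test: "We conducted two-sample t-tests on the change in the mean score for each of our outcomes".

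The power paragraph at the end of the Analysis section states that "we assumed an alpha of 1% and a power of 80" per cent. It continues: "For our final analysis sample of N=936, comparing the two posters we can detect" three differences, one per primary outcome. For this outcome the entry is "a 0.8 percentage point difference in accuracy of perceived pregnancy risk (standard deviation of 0.05"). The entries for knowledge (3 points, SD 0.18) and method effectiveness (6 points, SD 0.35) each carry a reference number for the SD; this one does not.

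Neither the sidedness of the 1% alpha nor the allocation ratio is given. On allocation, the Study Design section says only: "Participants will then be randomly shown one of the two fact sheets".

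**The concern.** On a −1/0/+1 scale the SD cannot be chosen independently of the effect. A mean change away from zero requires some women to change status, and those women create variance. An SD of 0.05 with a mean change near zero means that 0.05² = 0.25% of women change status, about 2 of 936. Yet a 0.8-point difference arising in one arm of 468 already means 0.008 × 468 = 3.7 net changers in that arm alone.

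This sentence is the only statement in the documents of what the poster comparison can detect on this outcome. A reader who relies on it to interpret a null result would believe that differences of about one point had been looked for with good power, when the comparison is far less sensitive than that.

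**Working it through.** **Inputs.** From the Analysis section: alpha 1%, power 80%, N=936, SD 0.05, difference 0.8 points. From the Measures section: a 0/1 score analysed as change. Assumed: 468 women per poster, and two-sided alpha unless stated otherwise.

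**1. Reproducing the stated figure.** For two means, detectable difference = (z_alpha + z_power) × SD × sqrt(2/n).

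- Two-sided 1%: (2.576 + 0.842) × sqrt(2/468) = 0.2234 × SD
- One-sided 1%: multiplier 0.2071

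| Outcome | SD | Stated (points) | Two-sided 1% | One-sided 1% | 936 per arm, two-sided 1% | One-sided 5% |
|---|---|---|---|---|---|---|
| Knowledge | 0.18 | 3 | 4.0 | 3.7 | 2.8 | 2.9 |
| Accuracy of perceived risk | 0.05 | 0.8 | 1.12 | 1.04 | 0.79 | 0.81 |
| Method effectiveness | 0.35 | 6 | 7.8 | 7.2 | 5.5 | 5.7 |

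None of the three stated values follows from the stated inputs. All three appear, after rounding, if 936 is used as the size of each arm or if alpha is one-sided 5%. Neither matches the text. With SD 0.05 accepted, power for 0.8 points is 45%, and 80% power would need 1,826 women in total.

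**2. Can SD 0.05 and 0.8 points coexist?** For a −1/0/+1 score with mean m, variance = share changing − m². The share changing is at least |m|, so variance ≥ |m|(1 − |m|).

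- With equal arms whose means differ by d, the smallest pooled variance is d(1 − d)/2. It is reached when one arm has mean 0 and the other changes in one direction only.
- For d = 0.008: sqrt(0.008 × 0.992 / 2) = **0.063**, above 0.05.
- Conversely, d(1 − d)/2 = 0.05² = 0.0025 gives d = **0.0050**, i.e. 0.50 points. The other root, about 99.5 points, would need one poster to change almost everyone and the other almost no one.
- Rounding does not help at equal allocation: 0.75 points needs SD 0.061, while an SD that rounds to 0.05 is at most 0.055.
- Reading 0.05 as the SD of a single 0/1 score gives the same bound.

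Alpha, power and sidedness do not enter this step.

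**3. What the test delivers in the most favourable case.** Suppose one poster changes nobody and the other changes k of 468 women, all in one direction.

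- Two-sided 1%: k = 6 gives t = 2.46, p = 0.014; k = 7 gives t = 2.66, p = 0.0079. At least 7 changers are needed.
- P(Binomial(468, 0.008) ≥ 7) = 8.5%. The probability reaches 80% at 0.0193, i.e. 1.93 points, or 1.93/0.8 = 2.4 times the stated value.
- One-sided 1%: 6 changers are needed, power at 0.8 points is 17.6%, and 80% power is reached at 1.68 points (2.1 times).
- Splitting the changers between posters in opposite directions gives 1.93 to 1.94 points. Adding background changers of 0.02% to 0.2% per direction gives 2.0 to 2.8 points, with power at 0.8 points of 7% to 9% (both two-sided).

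The normal approximation with SD fixed at 0.063 gives 26% power at 0.8 points. With the variance tied to the difference, it gives an 80%-power point of r/(1 + r) with r = 3.418²/468, i.e. 2.4 points. It is inaccurate with so few changers, so the exact figures are preferred here.

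**4. Illustration with assumed shares** (mean change near zero, two-sided 1%, 0.2234 × sqrt(share)):

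| Share changing (assumed) | SD | Detectable difference |
|---|---|---|
| 5% | 0.22 | 5.0 points |
| 10% | 0.32 | 7.1 points |
| 20% | 0.45 | 10.0 points |

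Simulated 80%-power points of the t-test are 4.9, 6.9 and 9.9, so the formula is adequate at these shares.

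**The case against.** **The bound is conditional.** The plan does not call the 0.05 pooled and does not give the allocation. If w is the smaller arm's share, the minimum pooled SD is sqrt(w × d × (1 − d)), and the two figures fit together once w is about 31.5% or less (0.0025 / (0.008 × 0.992)). At 40/60 the bound is 0.056, and it falls to 0.0546 if 0.8 is a rounded 0.75. This stands as a condition, but nothing in the documents suggests such a split, and unequal arms worsen the shortfall in step 1 (by about 2% at 40/60).

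**The 0.05 could be the SD in one arm only.** Means of −0.25 and +0.55 points would give one arm an SD of 0.05 and a difference of 0.8 points. The pooled SD is then sqrt((0.0025 × 0.9975 + 0.0055 × 0.9945)/2) = 0.063, so the two-sample formula would have been given the wrong SD.

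**The formula error is the broader defect.** The ratio of stated difference to SD is 0.16 to 0.17 for all three outcomes (0.8/5, 3/18, 6/35), which points to one shared formula with a wrong n or alpha. That is fair, and the fix covers it. The SD problem remains after the formula is corrected. A decimal slip (SD 0.5 and 8 points) would keep the same ratio, but that is conjecture; only the authors can say.

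**Little hangs on the sentence.** It takes N as given and drove no design decision, and a confidence interval would show what a null result excludes. Both are true and they limit the consequence, but the stated figure is still wrong.

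**Conclusion.** The concern holds. Given the plan's own scoring and test, SD 0.05 and a 0.8-point difference are incompatible: 0.8 points needs a pooled SD of at least 0.063, and SD 0.05 allows at most 0.50 points. This rests on roughly equal arms and on 0.05 being the SD that enters the two-sample comparison.

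Separately, the stated alpha, power and N do not give 0.8 points even at SD 0.05, nor do they give the stated 3 and 6 points for the other outcomes, under either sidedness. The smallest realistic correction for this outcome is a factor of about 2. If 5% or more of women change status, which is an assumption, it is a factor of 6 or more (5.0/0.8). The validity of the trial is not in question; its stated sensitivity on this primary outcome is.

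**What to change.** Replace SD 0.05 with sqrt(share changing − mean change²). Take the share from the study data pooled over both posters, use that share and not the observed difference between posters, and label the result as computed after data collection. Possible wording:

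> With X% of women changing accuracy status (posters pooled, calculated after data collection), N=936 (n1 and n2 per poster) gives 80% power at [one/two]-sided alpha 1% for a Y percentage point difference in mean change in accuracy of perceived pregnancy risk.

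If the observed share is not used, give a range labelled as assumed, such as the 5%, 10% and 20% rows above. In either case, state the sidedness and the number of women per poster, and recompute all three detectable differences with one two-sample formula at the stated alpha.

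The cost is a reworded power statement with less favourable figures. Design, sample size and tests do not change.
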